### **3.2.2 Training**

Both groups will participate of 14 individual treatment sessions, with physiotherapist supervision, twice a week, for seven weeks. Each treatment session will be composed of 30 minutes of regular physical therapy (equal to both groups), based on stretching, strength and mobility exercises, followed by 30 minutes of balance training using a gaming system with balance board device (eight games of Nintendo Wii Fit®, for games per session).

Differences between groups are based on the type of physiotherapist's role in the training:

Virtual Reality Training Without Physiotherapeutic Intervention (Experimental Group) will perform a balance training program in a virtual environment (using a gaming system with balance board device - eight games of Nintendo Wii Fit®, for 14 sessions)

without verbal/manual physiotherapeutic intervention. Initially, physiotherapist will provide instructions about the rules and strategies of how to play the game and control the avatar. Then the patient will be invited to start the game, and in the two attempts of the training no manual or verbal assistance will be provided by the physiotherapist. Physiotherapist participation during training will be restricted to ensuring patient safety, providing motivational verbal stimuli, and replicating the feedback provided by the game at the end of each attempt.

Virtual Reality Training With Physiotherapeutic Intervention (Control Group) will perform a balance training program in a virtual environment (using a gaming system with balance board device - eight games of Nintendo Wii Fit®, for 14 sessions) with verbal and manual physiotherapeutic intervention. Initially, physiotherapist will provide instructions about the rules and strategies on how to play the game and control the avatar. Then the patient will be invited to start the game, and in the first attempt of the training physiotherapist will provide manual and verbal assistance, providing corrections on movement speed, direction, acceleration, amplitude, rhythm and coordination, necessary to achieve game goals (avoiding compensatory movements). In the second attempt, no manual or verbal assistance will be provided by the physiotherapist (only ensuring patient safety and providing motivational verbal stimuli, and replicating the feedback provided by the game), allowing the patient to organize his or her performance.

There will be eight games (four per session) by Nintendo Wii Fit®, selected according to the motor requirements of static and dynamic balance.

### **3.3 Statistical Analysis**

Demographic data and clinical characteristics of the control and experimental groups will be compared using the unpaired T-test.

Results of the primary and secondary measures will be analyzed after normality test (Kolmogorov-Smirnov test), with repeated measures of variance (ANOVA), one for each dependent variable, using as a factor group (GC and GE) and the three evaluations (before treatment, after treatment and follow up), the last measure being repeated (2x3 RM-ANOVA).

The Tukey Post Hoc Test will be performed to verify any differences between effects with significance.

Significance level adopted: 5%.

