### **3. Methods**

It will be a prospective, single blinded, randomized clinical trial, performed at Center of Research of the Department of Speech Therapy, Physical Therapy and Occupational Therapy of São Paulo University.

Forty chronic stroke patients will be randomly in control and experimental group, 20 each one. Both groups conduct 14 training sessions, twice a week, for seven weeks. Each session will consist a 30 minute-global-exercise series including stretching, muscle strength and axial mobility exercises. After this, both groups will perform 30 more minutes of balance training using eight Wii Fit® games which stimulate motor and cognitive functions.

Patients will be assessed at the beginning, in the end and 60 days after the end of the treatment (follow-up).

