#### **3.1 Participant allocation**

Patients will be randomized in two groups: Experimental Group or Control Group. Each participant must sign the Consent Form.

Forty patients will be selected according to the following criteria:

Inclusion Criteria:

- hemiparetic status resulting from a single stroke at least 6 months earlier;
- the ability to walk 10 m independently with or without an assistive device;
- a Montreal Cognitive Assessment (MoCA) score of  $\geq 20$ ;
- the absence of a musculoskeletal condition that could potentially affect the ability to stand or walk safely;
- absence of serious visual impairment or a hearing disorder;
- muscle strength  $\geq 3$  in lower limbs;
- ability to understand and follow simple instructions.

Exclusion Criteria:

- severe dementia or aphasia;
- hemispatial neglect, ataxia or any other cerebellar symptom;
- inability to stand without minimal assist;
- uncontrollable medical complications;
- participation in other studies or rehabilitation programs.

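### Baseline groups are compared by unpaired t-test, which tells the reader nothing useful in a randomised trial of 20 per arm, while the outcome model makes no adjustment for baseline

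*Combined protocol and SAP*

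**What the plan says.** Section 3.3 (Statistical Analysis) gives one method for all baseline data: "Demographic data and clinical characteristics of the control and experimental groups will be compared using the unpaired T-test". It does not list the variables, name a method for categorical or ordinal items, or say what follows from a significant or non-significant result. The normality check in that section is stated only for the primary and secondary measures.

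The same section analyses each outcome "with repeated measures of variance (ANOVA), one for each dependent variable, using as a factor group (GC and GE) and the three evaluations". The three evaluations are before treatment, after treatment and follow-up, so the baseline score is a response level and not a covariate. No other covariate is named. Tukey comparisons follow significant effects, at a 5% level.

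On design, section 3 (Methods) says "Forty chronic stroke patients will be randomly in control and experimental group, 20 each one", and section 3.1 says only "Patients will be randomized in two groups: Experimental Group or Control Group". No stratification, blocking or minimisation is described.

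**The concern.** In a properly randomised trial any baseline difference between arms is a chance difference, so a test of whether it is due to chance answers a question whose answer is known. What matters is how large the observed imbalance is on a variable that predicts outcome, and what the outcome analysis does about it. A t-test with 20 per arm stays silent over the range of imbalance that chance commonly produces. A column of non-significant p-values could then be taken as showing that the arms are comparable.

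The outcome model does not fill the gap. Following change from baseline, as the group-by-visit term does, subtracts the whole baseline difference. Unless the visits are perfectly correlated, that over-corrects: the arm that starts lower tends to gain more through regression to the mean alone. Adjusting for baseline as a covariate subtracts the right amount and gives a more precise estimate. In a trial of 40 patients that precision is worth having.

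A lesser point is that a t-test has no meaning for a nominal variable with three or more categories, and the plan offers no alternative.

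**Working it through.** **Inputs.** From the documents: 20 per arm (section 3), 5% level (section 3.3), no covariates (section 3.3). Assumed: two-sided testing, approximate normality, equal SD at each visit, and a correlation r between baseline and a later visit of 0.5 to 0.9. The documents give no correlation, so the range is shown. The plan's only figure, 40 patients, comes with no effect size, SD or power and cannot be reproduced.

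**Step 1: what the t-test can flag.** The standardised difference in baseline means has standard error sqrt(2/20) = 0.316. The 5% critical value of t on 38 df is 2.024. The smallest observed imbalance that reaches p<0.05 is 2.024 × 0.316 = 0.64 SD. An observed 0.5 SD gives t = 0.5/0.316 = 1.58 and p = 0.12, so it is never flagged.

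**Step 2: what chance produces.** The probability that one given variable differs by more than d is 2 × (1 − Φ(d/0.316)).
- d = 0.3: d/0.316 = 0.949, probability 0.343.
- d = 0.5: d/0.316 = 1.581, probability 0.114.

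**Step 3: effect on a change-from-baseline contrast.** Take an observed imbalance d = 0.5 SD and no treatment effect. The later visit is expected to differ by r × d, so the change differs by (r − 1) × d. Given d, the change contrast has variance (2/20)(1 − r²). The analysis judges it against the critical value 1.96 × sqrt((2/20) × 2(1 − r)). Conditional type I error follows from the normal distribution. For r = 0.5 the bias is −0.25, the conditional SD is sqrt(0.075) = 0.274 and the critical value is 0.620. The two tail areas are Φ((−0.620 + 0.25)/0.274) = 0.088 and 1 − Φ((0.620 + 0.25)/0.274) = 0.001, together 0.089 before rounding.

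**Step 4: precision.** The variance of the change contrast is (2/20) × 2(1 − r) and of the baseline-adjusted contrast (2/20)(1 − r²). Their ratio is 2/(1 + r), so adjustment with 20 per arm is as precise as a change-score analysis with 20 × 2/(1 + r) per arm.

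| r | Bias of change at d = 0.5 (SD) | Conditional type I error | Equivalent n per arm with adjustment |
|---|---|---|---|
| 0.5 | −0.25 | 0.089 | 26.7 |
| 0.7 | −0.15 | 0.075 | 23.5 |
| 0.8 | −0.10 | 0.067 | 22.2 |
| 0.9 | −0.05 | 0.058 | 21.1 |

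Baseline adjustment has no such bias and holds the conditional error at 0.05 throughout. At a smaller imbalance of 0.3 SD the conditional error of the change contrast is 0.046 to 0.049, slightly below nominal. The excess therefore belongs to the larger imbalances.

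**Step 5: t-test on categorical items.** For a 0/1 item, all 441 possible tables with 20 per arm were enumerated. The t-test and the uncorrected chi-square give the same 5% decision in every one. The t-test and Fisher's exact test differ in 28. At 6/20 against 13/20, for example, the t-test gives p = 0.027 and Fisher p = 0.056.

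**The case against.** The strongest reply is that the baseline sentence concerns only a descriptive table. It does not claim that the t-test protects the result or triggers adjustment, and the group-by-visit term already removes part of any baseline difference. This largely stands. It limits the point to conditional bias and precision, but it does not make the p-values informative or the adjustment less worthwhile.

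Several stronger readings are tempting and are not supported:

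- **The t-test catches a 0.5 SD imbalance about a third of the time.** The 34% figure is power against a true population difference, which randomisation rules out. An observed 0.5 SD is never flagged.
- **The wrong test will distort the baseline table.** The plan lists no baseline variables. Use of a walking aid appears only as an eligibility condition ("with or without an assistive device", section 3.1), and sex is not mentioned. For 0/1 items the numerical harm is small. The objection has force only for nominal items with three or more categories, and none is named.
- **The treatment comparison is biased by 0.40 SD.** With r = 0.7 and a 0.5 SD imbalance, the group main effect averaged over three visits is off by (0.50 + 0.35 + 0.35)/3 = 0.40 SD. That term averages in a pre-treatment visit. A differential response to treatment appears in the group-by-visit term, for which the figure is −0.15 SD. Section 3.3 does not say which term is decisive, but that is a separate matter.
- **The false-positive rate of the trial is inflated.** Averaged over all randomisations it remains 5%.

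**Conclusion.** The point holds in a limited form. Baseline significance tests are uninformative here, and the planned outcome model passes over a baseline adjustment that the collected data already allow. For an observed 0.5 SD imbalance, which about 11% of trials would exceed on a given variable, a change-from-baseline contrast is biased by −0.25 to −0.05 SD, with conditional type I error of 0.089 to 0.058. The precision forgone relative to adjustment amounts to about 1 to 7 patients per arm.

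The bias, conditional error and precision figures rest on assumed visit correlations of 0.5 to 0.9, normality and equal variances. They describe a contrast of baseline with one later visit, which is a component of the three-visit interaction and not the whole test. The change should be made before analysis, but the trial is not invalid without it.

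**What to change.** Two sentences in section 3.3 need to change together. A model cannot adjust for baseline while baseline remains one of its response levels, so editing only the baseline sentence would not be enough.

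1. **Baseline table.** Summarise each characteristic by arm with statistics suited to it (mean and SD, median and interquartile range, or count and percentage), without significance tests.
2. **Outcome model.** Replace the 2x3 repeated-measures ANOVA with a baseline-adjusted model fixed in advance, whatever imbalance is observed. This could be ANCOVA, or a mixed model with the post-treatment and follow-up scores as responses, arm, visit and their interaction as factors, and the outcome's own baseline score as covariate. Between-arm contrasts at each of the two visits replace the Tukey comparisons across three visits.

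The cost is one degree of freedom per model, a rewritten model and contrast specification, and no p-value column in the baseline table. No new data are needed, because both groups are already assessed before treatment (section 3.2.1).

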## **1. Background**

Stroke is the leading cause of death in some countries and the leading cause of disability in the world (Roger 2012; Adamson 2004; *The Internet Stroke Center* 2016), significantly contributing to the increase in public health costs. In Brazil, approximately 50% of the people affected present some degree of disability (Carmo 2015) and are dependent on others due to the injury (Allen 2009; Corrêa 2005).

Patients present less symmetry between lower limbs and difficulty in weight bearing on the affected side in standing position, with consequente change in the motor function, balance and gait (Trindade 2011).

Actually there are several approaches to rehabilitation and, between then, virtual reality (VR) - technology that promotes human-computer interaction in an created environment (Laver, 2012) – is expanding in the treatment of post-stroke balance disorders, because VR promotes a motivated, challenging, task-specific and repetitive training (Chen 2016, Laver 2012; Yatar 2015; Joo 2010; Saposnik 2011). The commercial equipment Nintendo Wii Fit®, promote anterior, posterior and lateral excursiono f the center os pressure, allowing greater postural control and symmetry, besides, providing cognitive demand of the decision making to perform the motor task effectively (Crosbie, 2007; Broeren, 2008; Joo, 2010; Cameirão, 2011).

Some studies report the possibility of using this system at home, where the training could be carried out autonomously by the patients themselves, without a physiotherapist directing the training (Yatar 2015; Sugarman 2009; Deutsch 2009). However, as suggested by Yatar in 2015, this issue still controversial - different authors cite the possibility of training without supervision of the physiotherapist but discuss the lack of evidence, questioning the need of the presence of the physiotherapist intervening in the treatment, in order to guarantee patient motivation and safety (Joo 2010, Borghese 2013, Laufer 2014). Thus, there is a need to clarify the role of physical therapist assistance during balance training through VR in comparison to that performed without intervention.

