## **2. Purpose**

The aim of this study is to compare the effects of a balance training program in a virtual environment (using a gaming system with balance board device) with and without

verbal/manual physiotherapeutic intervention, on the motor function, balance and gait in chronic stroke patients.

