### **3.2 Procedures**

#### **3.2.1 Assessments**

Both groups will be assessed before treatment, after treatment and after 60 days of the end of the treatment (follow-up).

Primary outcomes:

- The lower limb subscale of the Fugl-Meyer Assessment (FMA-LE): FMA-LE is a subscale measuring lower limb motor recovery. It examines movement and coordination of the hip, knee, and ankle in the supine, sitting, and standing positions. Each item is scored on a 3-point scale (0, cannot perform; 1, partially performs; 2, performs fully). The score range is 0 to 34, with higher scores indicating better lower limb motor performance (Fugl-Meyer, 1975; Maki, 2006).
- Balance Evaluation Systems Test (BESTest): Balance Evaluation Systems Test (BESTest) measures balance. It includes 36 items that evaluate performance of
  - 6 balance systems: biomechanical constraints, stability limits/verticality, anticipatory postural adjustments, postural responses, sensory orientation, and stability in gait (Horak, 2009).
  - 6-minute walk test: The 6MWT is a practical simple test. This test measures the distance that a patient can quickly walk on a flat, hard surface in a period of 6 minutes (the 6MWD). The 6MWT has been used as a measure of functional status of patients (Britto, 2006).

Secondary outcomes:

- Limits of Stability: The Limits of Stability subtest quantifies the maximum distance a person can intentionally displace their center of pressure (COP) from start position of midline COP centered over the base of support to eight targets.

Location and movement of the COP was indicated by a cursor display projected on a screen in front of the subject. As targets were highlighted, the subject was to move the COP cursor quickly and accurately as possible towards a target located on the Limits of Stability perimeter and hold position as close to the target as possible. The parameters include COP movement velocity and directional control (% to target).

- Rhythmic Weight Shift: The Rhythmic Weight Shift quantifies the subject's active weight shift ability by moving the COP cursor to match velocity and direction of a moving visual target in the medial- lateral (ML) and anterior-posterior (AP) directions at three different velocities.

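### Section 3.3 tests each outcome with a 2x3 RM-ANOVA but plans no between-group difference or confidence interval; a baseline-adjusted estimate would answer the trial's question better from the same data

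*Combined protocol and SAP*

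**What the plan says.** The purpose (section 2) is a comparison: "The aim of this study is to compare the effects of a balance training program in a virtual environment" with and without physiotherapist intervention. The experimental arm is the one without manual or verbal assistance (section 3.2.2). The Background explains the interest: some studies raise the possibility of home use, "where the training could be carried out autonomously by the patients themselves, without a physiotherapist directing the training".

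Section 3 sets the size: "Forty chronic stroke patients will be randomly in control and experimental group, 20 each one". Section 3.2.1 sets the visits: "Both groups will be assessed before treatment, after treatment and after 60 days of the end of the treatment (follow-up". It also lists three primary outcomes: FMA-LE, BESTest and the 6-minute walk test.

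Section 3.3 is the whole analysis plan. After t-tests on baseline characteristics and a normality check, primary and secondary outcomes are analysed "with repeated measures of variance (ANOVA), one for each dependent variable, using as a factor group (GC and GE) and the three evaluations". The levels of the time factor are "before treatment, after treatment and follow up), the last measure being repeated (2x3 RM-ANOVA". Then: "The Tukey Post Hoc Test will be performed to verify any differences between effects with significance". The level is 5%. Neither this section nor any other names a between-group estimate, a confidence interval or the visit at which the arms are contrasted.

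**The concern.** A trial that compares two ways of delivering the same training should report how far apart the arms are and how precisely that is known. The plan specifies tests only. If neither the group effect nor the group-by-time interaction is significant, the Tukey step as written is not triggered for the arms, and nothing prespecified describes the size of the difference. If only the time effect is significant, Tukey compares visits, not arms.

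There is also a question of efficiency. With baseline as an outcome level, a treatment effect appears in two places. In the group main effect it is diluted, because the arms are expected to be equal before treatment. In the group-by-time interaction it is tested on 2 degrees of freedom, without baseline as a covariate. With 20 per arm, that could cost power that the data already collected would provide.

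An estimate can still be added after the fact, but the visit, the adjustment and the emphasis among three primary outcomes would then be chosen with the data in view.

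**Working it through.** **Inputs from the documents.** 20 per arm (section 3); three visits (section 3.2.1); 2x3 RM-ANOVA at 5% (section 3.3). The sample size of 40 comes without power, SD or effect size, so there is no calculation to reproduce.

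**Assumptions.** Results in SD units; equal SDs; equal correlation rho between any two visits, tried at 0.5, 0.7, 0.8 and 0.9; no dropout; two-sided 5%; arms equal at baseline, with a true deficit of 0.5 SD at both later visits.

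**Planned group-by-time F.** The difference profile (0, 0.5, 0.5) centred on its mean is c = (−0.333, 0.167, 0.167). The noncentrality is 20 × 2 × Σ(c/2)² / (1 − rho) = 40 × 0.04167 / (1 − rho) = 1.667 / (1 − rho), that is 3.33, 5.56, 8.33 and 16.67. The F has 2 and 76 df, with critical value 3.12.

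**ANCOVA at one visit.** SE = √(2/20 × (1 − rho²)) = 0.274, 0.226, 0.190, 0.138. The noncentral t has 37 df and noncentrality 0.5/SE = 1.83, 2.21, 2.64, 3.63.

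**ANCOVA on the mean of the two later visits.** The mean has variance (1 + rho)/2 and covariance rho with baseline, so the residual variance is (1 + rho)/2 − rho² = 0.50, 0.36, 0.26, 0.14. SE = √(2/20 × that) = 0.224, 0.190, 0.161, 0.118. Noncentrality = 2.24, 2.64, 3.10, 4.23.

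Chance of missing the 0.5 SD deficit:

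| rho | Planned group-by-time F | ANCOVA, one visit | ANCOVA, mean of two visits |
|---|---|---|---|
| 0.5 | 66% | 57% | 41% |
| 0.7 | 47% | 42% | 27% |
| 0.8 | 28% | 27% | 14% |
| 0.9 | 4% | 6% | 2% |

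**Check by simulation** (20,000 trials per setting). The planned F missed 65.9%, 47.0%, 27.8% and 4.3%, as in the table. Single-visit ANCOVA missed 58.4%, 43.2%, 28.0% and 6.9%, about one point more than the formula, which ignores chance baseline imbalance. At rho 0.8 the two are therefore level. With equal arms, the group-by-time F rejected in 4.7% to 4.9% of trials, so the planned test is valid.

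**Group main effect.** The difference averaged over three visits is (0 + 0.5 + 0.5)/3 = 0.33 SD. Simulated power was 24%, 21%, 20% and 18%, so this line of the ANOVA table is a weak guide to the treatment effect.

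**Precision at one visit** (95% CI half-width = t × SE, with t = 2.024 on 38 df or 2.026 on 37 df). Unadjusted: 2.024 × √(2/20) = 0.64 SD, whatever rho is.

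| rho | Change score | Baseline-adjusted |
|---|---|---|
| 0.5 | 0.64 | 0.55 |
| 0.7 | 0.50 | 0.46 |
| 0.8 | 0.40 | 0.38 |
| 0.9 | 0.29 | 0.28 |

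With 17 per arm (15% dropout, assumed), the half-width is 0.70 SD unadjusted and 0.61 to 0.31 SD adjusted over the same range of rho.

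**The case against.** The best defence is that the planned model is a recognised and valid analysis of this design, and that a short list of tests is not a promise to withhold estimates. Both points stand. A reader might infer that baseline as an outcome level makes the test invalid; it does not, and at rho 0.9 the planned F misses less often than single-visit ANCOVA (4% against 6%). Nor is between-group comparison ruled out, since Tukey tests after a significant interaction could compare the arms at a visit.

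A reader might also infer that a non-significant result will be taken to show that training without assistance is just as good. The documents do not support this. Section 2 is a neutral comparison, no margin is set, equivalence and non-inferiority are never claimed, and nothing says how a null result will be read.

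It is also fair to say that a change-score contrast could supply the missing estimate, with an interval almost as narrow at rho 0.8 or above, and that every size here depends on an assumed rho and deficit. The limited precision comes from 20 per arm, and reporting an interval shows it but does not remove it.

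None of this supplies a planned estimate. At rho 0.5 to 0.8, an analysis that adjusts for baseline and uses both later visits is clearly more sensitive than the planned F.

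**Conclusion.** The concern holds as a gap in the prespecified result and as a choice of a less efficient analysis. It is not an error in the test. Section 3.3 should be changed, but the trial remains interpretable if it is not.

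Under the stated assumptions, moving from the planned F to single-visit ANCOVA reduces the miss rate by 9 points at rho 0.5 (66% to 57%) and 5 at rho 0.7 (47% to 42%), and makes no useful difference at 0.8 or above. ANCOVA on the mean of the two later visits misses less than the planned F at every rho tried: 25 points less at 0.5 (66% to 41%), 20 at 0.7, 14 at 0.8 and 2 at 0.9. That advantage assumes the same deficit at both visits and would shrink if the effect faded by 60 days.

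The estimate and interval are missing whatever rho is. At high rho they are the main gain; at low to moderate rho there is also a gain in power.

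**What to change.** Add one paragraph to section 3.3. For each of the three primary outcomes, state that the treatment-effect result is the baseline-adjusted difference between arms, with its 95% CI, at end of treatment and at the 60-day follow-up. Estimate it from a repeated-measures model of the two post-baseline visits with baseline as covariate, or from one ANCOVA per visit. Report it whether or not any F test is significant. Keep the 2x3 RM-ANOVA as a supporting test. If the gain from using both visits is wanted as a test, name the average of the two visit differences as a contrast from the same model.

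The cost is a little more analysis, with no change to treatment, visits or sample size. It produces 3 × 2 = 6 intervals, each 95% on its own and not jointly. Some will be visibly inconclusive, because the half-width at one visit is still 0.28 to 0.55 SD after adjustment. If rho turns out to be 0.8 or more, single-visit adjustment adds little over a change-score interval (0.38 against 0.40 SD, and 0.28 against 0.29 SD).

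### The planned 2x3 RM-ANOVA carries the pre-treatment score as an outcome level, has no baseline covariate and names no deciding effect; a baseline-adjusted joint test of the two later visits is a cheap improvement

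*Combined protocol and SAP*

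**What the plan says.** The purpose (section 2) is to "compare the effects of a balance training program in a virtual environment" with and without the physiotherapist's intervention, so the question is one of a difference between groups. Section 3 sets the size: "Forty chronic stroke patients will be randomly in control and experimental group, 20 each one". Section 3.2.1 sets the visits: "Both groups will be assessed before treatment, after treatment and after 60 days of the end of the treatment (follow-up".

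Section 3.3 gives the analysis. Each outcome has its own ANOVA, "using as a factor group (GC and GE) and the three evaluations (before treatment, after treatment and follow up", with "the last measure being repeated (2x3 RM-ANOVA". The score before treatment is therefore one of the three levels of the outcome. No covariate is listed; the only other use of baseline data is a set of unpaired t-tests on demographic and clinical characteristics, which compares the groups but adjusts nothing. On which effect counts, the section says only this: "The Tukey Post Hoc Test will be performed to verify any differences between effects with significance". The 5% level is stated without being tied to any one effect. Effect size, SD, correlation and power are not given anywhere.

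**The concern.** A 2x3 RM-ANOVA yields a group F, an evaluation F and a group-by-evaluation F. Two of them involve group, and they answer different questions. The interaction asks whether the groups change differently. The group main effect compares averages over all three visits, including the one before any training has taken place. The plan leaves open which is meant, and the Tukey comparisons follow whichever effect is significant.

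The second point is efficiency. The interaction uses the baseline score only by subtracting it, which amounts to fixing its slope at 1. With 20 patients per group, estimating that slope from scores already scheduled can narrow the group comparison at no cost in patients or visits. At stake are some power and precision and a clear reading of the result, not the validity of the interaction test.

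**Working it through.** The documents state no figure that could be reproduced, so what follows is a comparison under stated assumptions.

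**Inputs.** From the documents: n = 20 per group (section 3), three visits (section 3.2.1), alpha 5% (section 3.3). Assumed: effect d = 0.5 SD, equal SDs, the same correlation ρ between all visits, no dropout; ρ ranges over 0.3 to 0.9.

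**What the group main effect estimates.** Randomised groups have equal expected baselines. For a sustained effect the visit differences are (0, d, d), and the group main effect estimates (0 + d + d)/3 = 2d/3. For an effect at one later visit only it estimates d/3.

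**Noncentrality for a sustained effect.**
- Group main effect, F(1,38): λ = (n/2)·3·(2d/3)²/(1+2ρ)
- Interaction, F(2,76): λ = n·d²/[3(1−ρ)]
- Baseline-adjusted joint test, F(2,36): λ = n·d²/[(1−ρ)(1+2ρ)], times about (1 − 1/38) for estimating the baseline slope

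At ρ = 0.5, n·d² = 20 × 0.25 = 5. The interaction has λ = 5/1.5 = 3.33. The joint test has λ = 5/(0.5 × 2) = 5.00, or 5.00 × 37/38 = 4.87. Before the slope factor, the ratio of joint test to interaction is 3/(1+2ρ): 1.50 at ρ = 0.5, 1.25 at 0.7, 1.07 at 0.9. Power:

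| ρ | 0.3 | 0.5 | 0.7 | 0.8 | 0.9 |
|---|---|---|---|---|---|
| Sustained effect: adjusted joint test | 42% | 46% | 60% | 75% | 96% |
| Sustained effect: interaction | 25% | 34% | 53% | 72% | 96% |
| One later visit only: adjusted joint test | 28% | 36% | 53% | 70% | 95% |
| One later visit only: interaction | 25% | 34% | 53% | 72% | 96% |
| Fading (0.5, 0.25) or growing (0.25, 0.5): adjusted joint test | 29% | 33% | 45% | 60% | 88% |
| Fading or growing: interaction | 20% | 26% | 42% | 58% | 88% |

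**Precision of the after-treatment difference.** Expected variance is (1−ρ²)(2/n)(37/36) on 37 df for the adjusted difference and 2(1−ρ)(2/n) on 76 df for the RM-ANOVA contrast. At ρ = 0.5 these are 0.75 × 0.1 × 37/36 = 0.077 and 0.100. The 95% CI half-widths, in SD and in the order of the table, are 0.62/0.56/0.46/0.39/0.28 adjusted against 0.75/0.63/0.49/0.40/0.28, with break-even at ρ of about 0.88.

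**Unequal correlations.** With a baseline-to-follow-up correlation 0.1 lower than the others (simulated), a growing effect gives the adjusted test 45% against 49% at ρ = 0.8 and 60% against 71% at ρ = 0.9. The uncorrected interaction has a type I error of 5.4 to 5.9% there; against a Greenhouse-Geisser-corrected interaction the loss is 2 to 7 points. At high ρ these differences come mostly from the unstructured covariance and should not be credited to baseline adjustment. For a fading effect at ρ = 0.9, the univariate interaction has 82%, an unadjusted multivariate interaction about 94% and the adjusted test 93%. For a growing effect at ρ = 0.9, the multivariate interaction has about 56%, below the adjusted test's 60%. Like for like, against the multivariate interaction, adjustment gains 2 to 13 points at ρ of 0.5 to 0.8 and is about level or better at 0.9.

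**If the group main effect were read as the treatment test.** Power for a sustained effect, under equal correlations, would be 29% at ρ = 0.3, falling to 19% at 0.9. If either F involving group could count as positive, the false-positive rate per outcome would be 1 − 0.95² = 9.75%.

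**The case against.** In a design with one visit before treatment and two after it, group-by-evaluation is the obvious reading of a purpose that compares training effects. That test is valid and unbiased, and one sentence naming it would close the ambiguity. A baseline score held as an outcome level is not itself a fault: a longitudinal model that constrains the groups to equal baseline means gains about as much as covariate adjustment. The rest is a choice between two valid tests that turns on a correlation the documents do not give, and chronic patients may well have highly correlated scores, where the gain vanishes. The covariate model also assumes a linear baseline slope, which a ceiling on a bounded scale such as the FMA-LE (0 to 34) could disturb.

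Most of this stands, and it sets the limits of the point. A reader might infer that the plan ignores baseline, that its analysis is biased, or that it runs at a 10% error rate. The documents support none of these. The interaction does use baseline, by subtraction. Nothing in section 3.3 says that the group main effect will be taken as the treatment test or that either F suffices, so the 19 to 29% and 9.75% figures show what the silence permits, not what is planned. What the objection does not remove is that the baseline scores are already scheduled and that, at low to moderate correlations, using them as a covariate gives a more powerful test for most effect patterns.

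**Conclusion.** The point holds as an improvement worth making, not as the correction of an error. For a sustained 0.5 SD effect with equal correlations, the gain over the interaction is about 16 points of power at ρ = 0.3 (41.5% against 25.3%), 12 at 0.5, 7 at 0.7, 3 at 0.8 and none at 0.9. It is small or slightly negative (up to about 2 points) for a one-visit effect, and negative by about 4 to 11 points, against the uncorrected interaction, for a growing effect at ρ of 0.8 to 0.9 with the lower baseline-to-follow-up correlation. Effect size, correlations and absence of dropout are all assumptions. That the deciding effect is unnamed is plain from the text. Confidence that the change would help in this trial is medium, because the sign of the gain depends on quantities that the documents do not give.

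**What to change.** At the least, name the deciding test in section 3.3 and state that the group main effect of the 2x3 RM-ANOVA is not a treatment test.

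Preferably, for each primary outcome, model the after-treatment and follow-up scores on group, visit, group-by-visit and that outcome's baseline score, with the baseline slope free to differ by visit, an unstructured within-patient covariance and a small-sample df method such as Kenward-Roger. Make the 2-df joint test of group over both visits the deciding test, report the adjusted group difference with a 95% CI at each visit, and keep the RM-ANOVA as supportive. The documents rank neither later visit above the other. If the investigators regard one as primary, they may name its adjusted difference instead, but a test of the after-treatment visit alone would have only 5% power for an effect confined to follow-up.

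The cost is SAP wording; no patient, visit or measurement is added. Error df fall from 76 to 36, with the losses given above. Multiplicity across the three primary outcomes is a separate matter and needs its own rule.
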